24.0 Process to Document Consent in Writing

24.1 Consult “SOP: Written Documentation of Consent (HRP-091)” for recommended procedures, and describe whether and how consent of the subject will be documented in writing:

Written consent will include participants' printed name, signature, and date from each of the person obtaining consent (e.g., research coordinator/study staff member), and the research participant on the last page. In addition, a copy of the consent form (paper or electronic) will be offered to the study participant.

24.2 If the research presents no more than minimal risk of harm to subjects and involves no procedures for which written documentation of consent is normally required outside of the research context, you can request that the IRB waive the requirement to obtain written documentation of consent (e.g., consent to participate is indicated by pressing a button for an online questionnaire – after the consent information is presented and before the questionnaire begins):

N/A

24.3 If you will document consent in writing, attach a consent document with places for signatures. If you will obtain consent, but not document consent in writing, please attach the consent script or text. Review “CHECKLIST: Waiver of Written Documentation of Consent (HRP-411)” to ensure that you have provided sufficient information. You should use “TEMPLATE CONSENT DOCUMENT (HRP-502)” to create the consent document or script:

Written informed consent and consent statement are attached.

25.0 Resources Available

25.1 Describe the resources available to conduct the research. For example, as appropriate:

- *Describe the PI's availability to supervise the research.*
- *Justify the feasibility of recruiting the required number of suitable subjects within the agreed recruitment period. For example, how many potential subjects do you have access to? What percentage of those potential subjects do you need to recruit?*
- *Describe the time that you will devote to conducting and completing the research.*
- *Describe your facilities.*
- *Describe the availability of medical or psychological resources that subjects might need as a result of an anticipated or unanticipated consequence of participation in the research.*
- *Describe your process to ensure that all persons assisting with the research are adequately informed about the protocol, the research procedures, and their duties and functions (e.g., training plans, detailed study notebooks).*

The organizational structure of the study team involves overall leadership by [name], who will assume full responsibility for all aspects of the project, including design and participant eligibility. [name] will oversee recruitment and retention of participants. He will also oversee and delegate to the Co-Investigators and other study team members the responsibility of training study personnel, consenting of participants, and data collection. The Research Coordinator(s) and Research Assistant(s) will be trained and supervised as appropriate for any delegated study procedures. Behavioral data analysis will be overseen by [name] and conducted by the Co-Is and the Statistician.

All staff involved in the conduct and/or monitoring of this study will have completed the IRB Human Subject Protection Training and Good Clinical Practice Training.

Documentation of training will be maintained. The PI will be responsible for continuous data and safety monitoring of all participants enrolled in this study. In terms of standard operating procedures, trained research staff members will administer all assessments.

Participants will be recruited from the community via flyers, word of mouth referrals, and electronic advertisements (e.g., Craigslist, Facebook). To the extent possible, we will attempt to minimize obstacles to participation. For example, travel barriers will be addressed by providing transportation to participants, and scheduling barriers will be minimized by offering a flexible session schedule. All methods and measures will be conducted using standard operating procedures, and all staff (including recruitment staff) will be provided with human subjects' research training. We have a history of successful recruitment of smokers and drug users. All participants will enroll on a voluntary basis and sign an IRB-approved consent form prior to study participation. Note that we have been successfully recruiting cigarette smokers in our community for the past 10 years and the demographics of participants have been stable.

22-432 Effects of narratives on demand for low and high ventilated cigarettes and substitution for alternative products.

As far as facilities, the Addiction Recovery Research Center (ARRC; Director, [name]) is part of the FBRI, located in Roanoke, Virginia. Multidisciplinary research projects include examining the effects of behavioral, pharmacological, and transcranial magnetic stimulation (TMS) interventions as potential therapies for alcohol, cocaine, and nicotine dependence as well as other health behaviors such as obesity. ARRC also develops potential computerized therapies, applies principles from behavioral and neuro-economics to the understanding of addiction, and assesses nicotine product abuse liability.

ARRC resides on the 3rd floor of the FBRI and consists of several laboratories for clinical research. ARRC has private offices, individualized computer testing and interview rooms. The lab has a ventilated, negative air pressure smoking laboratory that is equipped with computers and five additional behavioral booths, a dedicated TMS suite, and a conference room. The research space also includes an adjacent male and female restroom with one-way observation windows and connecting stainless steel specimen pass-through cabinets. Office space for PI [name], Co-Investigators, Project Coordinators, Postdoctoral Associates, and Research Coordinators/Assistants is provided in the FBRI. The ARRC office suite has a copy machine, fax machine, network printer, scanner, and storage space for participant files and supplies as well as comfortable waiting rooms with entertainment (e.g., magazines, television, etc.) for research participants.

VTCRC has a conference room, private offices, individualized computer testing and interview rooms plus a network printer and access to secured shared servers.

26.0 Multi-Site Research

Contact the HRPP for multi-site research (involving multiple institutions) and the details required for this section will be provided. Otherwise, indicate N/A.

N/A

**NCT: NCT05487625**

**Document date: 09/13/2022**

### ***Study Design and Statistical Analysis plan***

In a between-group within-subject repeated measures design, participants will be randomized to one of three groups (narrative, fact sheet, or control) and complete five ETM conditions, which include six trials assessing different cigarette prices: a) high-ventilated cigarette alone, b) low-ventilated cigarette alone, c) high- and low-ventilated cigarette with high-ventilated cigarettes increasing in price, d) high- and low-ventilated cigarette with low-ventilated cigarettes increasing in price, and e) usual, high- and low-ventilated cigarette with usual cigarettes increasing in price.

A within-between subject analysis of variance (ANOVA) will test for differences in substitution and demand measures between groups (narrative, fact sheet, and control) and condition (e.g., high-ventilated cigarettes alone). We will test for the interaction between group and condition, suggesting a difference in how each group responds to different conditions. Order effects will be included in all models to account for the balanced Latin square design for counterbalancing the ETM conditions within the session. We will perform post-hoc contrasts to compare groups, based on our hypothesis.

Additional analyses might be conducted.

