2.0 Objectives

2.1 *Describe the purpose, specific aims, or objectives of this study:*

Purpose: To compare the effects of narratives on demand for low and high ventilated cigarettes and substitution for alternative products in the Experimental Tobacco Marketplace.

2.2 *State the hypotheses to be tested:*

22-432 Effects of narratives on demand for low and high ventilated cigarettes and substitution for alternative products.

The primary hypothesis is that narratives will decrease purchases of ventilated cigarettes and increase purchases of alternative products compared to the control narrative (fact sheet).

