Behavioral economic demand analyses can be used to understand the level of motivation to consume a product on either an individual or small group level, including cigarettes (2,3). This level of analysis allows for experimental manipulations to be made on variables of interest. By quantifying how consumption decreases as costs increase to obtain and consume a product, important indices of demand are obtained. These indices can be grouped into two main measures of consumption, demand intensity and demand elasticity, which are associated with use level and dependence severity (3,4,5,6). Demand intensity is the amount of the commodity consumed when available at very low cost (approaching free), and demand elasticity quantifies the degree to which the individual is willing to increase monetary or effort-based expenditures to maintain the same level of consumption as costs increase. Elasticity of demand has been shown to be a characteristic of the drug itself and independent of drug dose for many drugs including nicotine (2,7,8).

22-432 Effects of narratives on demand for low and high ventilated cigarettes and substitution for alternative products.

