Substitution is defined as an increase in the consumption of a constant-priced product while the cost of a different commodity is increased. For example, we have shown that as the price of conventional cigarettes is increased and its consumption decreased, the consumption of nicotine gum increased even though its price remained constant (10). Substitution defines one end of a continuum of interactions between two commodities. At the other end of that continuum, commodities can also function as complements. Complementarity refers to the decreased consumption of a constant-priced product in response to an increase in the price of a different commodity. For example, the research team has previously shown that as the price of cigarettes increased, consumption of coffee decreased even though its price remained constant (11). Between these two extremes is independence, which occurs when changes in the price of one commodity have little or no effect on consumption of another commodity where price has remained unchanged. Substitution, complementarity, and independence are measured by cross-price elasticity of demand and are represented by values that are positive, negative, or near zero, respectively. Studies to date have almost exclusively examined only pairs of products and, in even fewer cases, three concurrently available commodities. For example, in one of our studies smokers had access to conventional cigarettes, denicotinized cigarettes, and nicotine gum¹³. When the price of conventional cigarettes increased, consumption of both denicotinized cigarettes and nicotine gum increased even though their prices were fixed. Thus, denicotinized cigarettes and nicotine gum functioned as substitutes for conventional cigarettes. Indeed, by concurrently using both products, the smoker could reproduce both the central and sensory effects of standard cigarettes by consuming the denicotinized cigarette (i.e., sensory effects) and nicotine gum (i.e., central effects). Importantly, denicotinized cigarettes functioned as a better substitute than gum (the use of denicotinized cigarettes increased the most). This effect could not have been predicted from the individual demand curves with these commodities. Only when they were measured together did these complex interactions emerge. Lastly, in this experiment consumption of conventional cigarettes was greatest

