22-432 Effects of narratives on demand for low and high ventilated cigarettes and substitution for alternative products.

potential benefits of quitting and transitioning to less harmful products. The results might inform tobacco control policies.

Study Endpoints

3.4 *Describe the primary and secondary **study** endpoints. See links below for discussion of study endpoints and how they may differ from study objectives. These are most common in clinical trials but are sometimes applicable to other types of biomedical research, as well as social, behavioral, or educational research. See link below for a discussion.*

https://docs.google.com/document/d/1Wocz7K7a0hCQJPPO_khh511SQQjhGDDGHzcOPRHR5Tw/edit?usp=sharing

Substitutability: the two groups will be compared to assess whether substitutability with tobacco products occurs as a function of the intervention and cigarette price.

3.5 *Describe any primary or secondary **safety** endpoints. These should be included for all studies that are greater than minimal risk. (Minimal risk: The probability and magnitude of harm or discomfort anticipated in the research that are not greater in and of themselves than those ordinarily encountered in daily life or during the performance of routine physical or psychological examinations or tests.):*

This study will recruit adults who regularly smoke high-ventilated cigarettes. This study's procedures are not designed to increase daily nicotine use and we do not anticipate any increased risk to participants directly from this study, although there are risks of nicotine use and these are included in the risk section of this protocol and consent.

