7.0 Procedures Involved

7.1 Describe and explain the study design:

In a between-group within-subject repeated measures design, participants will be randomized to one of three groups (narrative, fact sheet, or control) and complete questionnaires on a computer, sample a range of tobacco products, and complete ETM conditions. Specifically, participants will purchase tobacco products in an online store under five ETM conditions, which include six trials each assessing different cigarette prices: a) high-ventilated cigarette alone, b) low-ventilated cigarette alone, c) high- and low-ventilated cigarette with high-ventilated cigarettes increasing in price, d) high- and low-ventilated cigarette with low-ventilated cigarettes increasing in price, and e) usual, high- and low-ventilated cigarette with usual cigarettes increasing in price.

7.2 *Provide a description of:*

- *All research procedures being performed*
- *If the study has more than one procedure, session, and/or subject population, describe each procedure, session, and/or study population separately. For complex studies, you are encouraged to include a figure or chart.*

Participants will complete 1) an informed consent and assessment session, 2) an ETM session, and a 3) follow-up session. Session 1 and 2 will be separated by an at home sampling phase and Session 2 and 3 will be separated by an at home product use phase.

1) In the consent and initial assessment session, participants will go through standard consent procedures and then provide a breath to confirm recent levels of smoking. Participants will complete a timeline follow back to assess previous month recent smoking, and consumption of nicotine products, and to determine ETM budget. A survey will administer demographics questions and nicotine/tobacco-related assessments (Wisconsin Index of Smoking Dependence Motives, Fagerstrom Test of Cigarette Dependence, Minnesota Nicotine Withdrawal Scale, Perceived Health Risk ratings). At the end of the session, participants will experience a trial of the ETM that will be used in the next session.

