For the sampling phase, participants will be provided two days worth of study cigarettes based on their number of cigarettes smoked per day, half of high-ventilated cigarettes and half of low-ventilated cigarettes. Participants will also be provided with a sample of other commercially available tobacco product to try. Participants will be instructed the order in which to use the products on the next three days. The order will be counterbalanced across participants.

During the sampling phase, participants will receive text messages asking how many of each product they sampled during those days.

2) Before the ETM session, participants will be randomized to the narrative, the fact sheet or the control group. In the ETM session, they will listen to a recording of a narrative of an individual who quit tobacco products or a fact-sheet with overall rates of smoking and its negative consequences. Participants in the control group will not be exposed to any recording. Then, participants will buy tobacco products to use throughout the next 7 days. Participants will complete a total of 30 purchasing trials each for 7 days' worth of products. They will be exposed to 5 conditions with cigarettes increasing in price. A balanced Latin square design will be used to present the following conditions: a) a) high-ventilated cigarette alone, b) low-ventilated cigarette alone, c) high- and low-ventilated cigarettes with high-ventilated cigarettes increasing in price, d) high- and low-ventilated cigarettes with low-ventilated cigarettes increasing in price, and e) usual, high- and low-ventilated cigarettes with usual cigarettes increasing in price. Additionally, participants will complete the Questionnaire on Smoking Urges-Brief, the Product Evaluation Scale, questions about the cigarette harshness, items of the Transport Narrative Questionnaire (narrative and fact sheet groups only), the Positive and Negative Affect Schedule

22-432 Effects of narratives on demand for low and high ventilated cigarettes and substitution for alternative products.

(narrative and fact sheet groups only), a manipulation check and an open-ended question about the recording they listened (narrative and fact sheet groups only), and the Experiment/Experimenter Attitudes Rating Scale.

For the seven days following the ETM session, participants will be asked not to use or purchase any outside tobacco/nicotine products and not to sell or give away any of their purchases.

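### The ANOVA leaves out baseline cigarettes per day, which probably costs precision for group contrasts on purchase quantities and demand intensity, and it states no protection against non-sphericity over five conditions

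*SAP*

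**What the plan says.** The SAP, and the Protocol's Study Design and Statistical Analysis Plan (item 4.2) in the same terms, give one model: "A within-between subject analysis of variance (ANOVA) will test for differences in substitution and demand measures between groups" (narrative, fact sheet, control) and conditions. It includes the group-by-condition interaction and order effects, followed by post-hoc group contrasts. Neither document names a baseline covariate, a sphericity correction, a multivariate test or a covariance structure.

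On baseline use, the Protocol says:

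- Session 1 (item 7.2): "Participants will complete a timeline follow back to assess previous month recent smoking, and consumption of nicotine products, and to determine ETM budget".
- Sampling phase (item 7.2): participants receive "two days worth of study cigarettes based on their number of cigarettes smoked per day".
- Session 2 (item 7.2): "Before the ETM session, participants will be randomized to the narrative, the fact sheet or the control group". Baseline use is therefore known before allocation.
- Eligibility (item 11.2): at least 10 cigarettes per day, with no upper limit.
- Background (3.1): the demand indices are "demand intensity and demand elasticity, which are associated with use level and dependence severity".

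The hypothesis (item 2.2) concerns purchases of ventilated cigarettes and of alternative products, narrative against fact sheet. The only listed endpoint (item 3.4) is "whether substitutability with tobacco products occurs as a function of the intervention and cigarette price", and the Background states that "Substitution, complementarity, and independence are measured by cross-price elasticity of demand". The sample size (item 13.1) rests on an interaction test with three groups, two measurements per participant, f = 0.25, 95% power and alpha 0.01.

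**The concern.** **Covariate.** A heavier smoker has more to buy for a week, and the same interview fixes both the recorded use level and the budget. Person-to-person differences in use therefore probably make up part of the error variance in purchase quantities and demand intensity. A pre-randomisation covariate can remove that part. Randomisation keeps the unadjusted contrasts unbiased, so only precision is at stake. It is still worth having: about 30 people per group (if allocation is equal; no ratio is stated) at alpha 0.01 leaves little power for a moderate pairwise difference.

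**Sphericity.** The classical F tests for condition and for group by condition assume that all pairwise differences between conditions have equal variance. With the two measurements used for the sample size this cannot fail. With five conditions it can, and the design gives a reason to expect it. Conditions a and c raise the price of the high-ventilated cigarette, b and d that of the low-ventilated one, and e that of the usual brand. Same-product pairs may well correlate more strongly than the others. An uncorrected test would then reject too often, and the interaction is the effect on which the study is sized.

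**Working it through.** **1. The plan's own figure.** For the interaction with k = 3, m = 2 and N = 90, lambda = f² × N × m / (1 − rho). With f = 0.25 and an assumed rho of 0.5 (not stated), lambda = 0.0625 × 90 × 2 / 0.5 = 22.5. On 2 and 87 df at alpha 0.01 this gives power 0.957. The smallest N is 88, or 90 in three equal groups, and 90 / 0.90 = 100. The stated numbers reproduce, but only for a two-level factor.

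**2. Covariate.** From the Protocol: alpha 0.01 and 90 completers. Assumed: 30 per group; d = 0.5 in units of the single-condition SD; rho, a common correlation between conditions; r, the correlation of baseline cigarettes per day with a person's mean cigarette purchases over the five conditions.

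- Variance of a five-condition mean: v = (1 + 4 rho)/5 = 0.6 at rho 0.5.
- Averaged contrast: SE = sqrt(2v(1 − r²)/30).
- Single-condition contrast: the covariate's correlation with one condition is r × sqrt(v), so SE = sqrt(2(1 − v r²)/30).
- Power: two-sided noncentral t with ncp = 0.5/SE, on 87 df unadjusted and 86 adjusted.

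At rho 0.5 and r 0.5, the single-condition SE falls from sqrt(2/30) = 0.258 (ncp 1.94) to sqrt(2 × 0.85/30) = 0.238 (ncp 2.10). The averaged SE falls from 0.200 to 0.173 (ncp 2.50 to 2.89).

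| rho 0.5, alpha 0.01 | unadjusted | r 0.3 | r 0.5 | r 0.7 |
|---|---|---|---|---|
| Single condition | 25% | 27% | 30% | 38% |
| Averaged over five | 45% | 50% | 60% | 80% |

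Sensitivity checks:

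- At r 0.5 with rho 0.3 or 0.7, the single-condition figure goes from 25% to 29% or 32%. The averaged figure goes from 61% to 77% or from 35% to 48%.
- At alpha 0.05 and rho 0.5, the single-condition figure goes from 48% to 50%, 55% or 63%.
- At r = 0, allowing 0.6% inflation of the SE, adjustment loses under one point: 24.9% to 24.6% single, 45.1% to 44.5% averaged.

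In 4,000 simulated trials (3 groups of 30, five conditions, r = rho = 0.5), the adjusted-to-unadjusted SE ratio was 0.93 for the single-condition contrast, 0.87 for the averaged contrast and 1.006 for an interaction contrast. The last shows no gain because a person-level covariate with one common slope cancels from differences between conditions.

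**3. Sphericity.** The interaction has (3 − 1)(5 − 1) = 8 df, with 87 × 4 = 348 error df before order terms. Under Box's approximation the uncorrected test's true error is P(F on 8 epsilon and 348 epsilon df > 2.563), where 2.563 is the nominal 1% critical value. This gives 1.3%, 2.0%, 3.0% and 4.0% at epsilon 0.9, 0.75, 0.6 and 0.5.

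A simulation of 20,000 null trials per scenario used equal variances, a ten-sequence balanced Latin square and position as a within-person factor. The correlations are assumed:

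| Same-product pairs / a,c against b,d / with e | epsilon | Uncorrected at 1% | Greenhouse-Geisser at 1% |
|---|---|---|---|
| 0.6 / 0.5 / 0.5 | 0.97 | 1.0% | 0.8% |
| 0.7 / 0.5 / 0.5 | 0.88 | 1.4% | 0.8% |
| 0.8 / 0.5 / 0.5 | 0.75 | 2.2% | 1.1% |
| 0.8 / 0.3 / 0.5 | 0.62 | 3.2% | 1.3% |

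Leaving out the order term changes nothing material (0.99%, 1.38%, 2.15%, 3.15% uncorrected). At nominal 5% the uncorrected test ran from 5.0% to 8.5% and Greenhouse-Geisser from 4.5% to 5.2%. An unstructured covariance with a Wald F on 8 and 87 df gave 1.2% to 1.3% at nominal 1% and 5.2% to 6.5% at nominal 5% (4,000 trials each), hence the advice to add a small-sample adjustment. Kenward-Roger itself was not simulated.

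**The case against.** Nothing in the text contradicts either part, so the case against is about weight.

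- **The covariate is an option, not a correction.** This stands. The gain is confined to outcomes outside the one listed endpoint, although purchases are the hypothesis and demand measures are in the SAP model.
- **r is unknown, and the floor of 10 per day trims the lower range, which may weaken it.** This stands; the cost cannot be stated as a single number. But if r is zero the loss from adjusting is under one point.
- **The larger gains belong to a contrast the SAP does not name.** This stands. High-ventilated cigarettes are not the product in condition b, nor low-ventilated ones in condition a, so a five-condition average is of total cigarette purchases and mixes the products the study means to separate. It also assumes the same effect in every condition. The single-condition figures are the safer guide, and there power stays low with or without adjustment.
- **Alpha 0.01 is set in the sample-size section, not in the SAP.** True, but it is set there expressly to control for multiple comparisons, and the gain also appears at 0.05.
- **No gain for the interaction holds only under a common slope.** Correct. A covariate-by-condition term could help if use level predicts purchases unevenly across conditions. That would be a further modelling choice.
- **Silence on sphericity does not mean the test will be uncorrected, and the milder scenarios show little inflation.** Both are fair. This part is closer to a missing detail than to an error. Leaving it open does, however, allow the choice to be made after the data are seen.

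**Conclusion.** Both parts hold, as improvements worth considering rather than faults that threaten the trial.

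The unadjusted group contrasts are valid but probably less precise than they need be. The single-condition gain at alpha 0.01 is about 2 to 13 percentage points of power for r between 0.3 and 0.7 (rho 0.5, d = 0.5, 30 per group, all assumed). It is larger only for an average over conditions that the SAP does not specify. No gain is to be expected for the interaction under a common slope, and little may follow for cross-price elasticity or for purchases of alternative products.

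The uncorrected interaction test can reach two to three times its nominal 1% rate if same-product conditions correlate at about 0.8 and the others at 0.3 to 0.5. It is close to nominal if correlations are nearly equal. The documents do not allow a choice between these cases. Between-group main effects, and single-degree-of-freedom contrasts with their own error term, are not affected.

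**What to change.** Add two or three sentences to the SAP.

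1. In the models for purchase quantities and demand intensity only, include baseline cigarettes per day from the Session 1 follow-back as a continuous main effect. Prefer it to the marketplace budget: both come from the same interview, but the rule that sets the budget is not stated. Say that the covariate is not expected to sharpen the group-by-condition interaction or the cross-price elasticity measures.
2. State that the multi-degree-of-freedom tests of condition and group by condition will use either a Greenhouse-Geisser correction or a mixed model with unstructured covariance and a small-sample adjustment such as Kenward-Roger. The mixed model is the natural choice if order enters as within-person position.

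The cost is one degree of freedom in the quantity and intensity models. The follow-back is already collected, so no new data are needed.
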